***Inclusion/Exclusion Criteria for Care Givers of Affected Patients:***

Inclusion criteria for telephone survey and potential care management are as follows:

- Family or informal caregiver (herein described as “caregiver”) of a person must be identified by that patient or self-identified as that individual who provides most of assistance among potentially other family members or friends of the care recipient (patient in the ED)
- For a caregiver to be eligible for inclusion the care recipient must be living in the community; however, later facility placement will not exclude that caregiver from continued participation.
- Caregiver must be English- or Spanish-speaking
- Caregiver must be able to speak on a telephone to be eligible for randomization
- Caregiver must have adequate hearing to communicate by phone
- Caregiver must demonstrate capacity to consent to research participation.
- Caregiver must be at least 21 years old

Exclusion criteria for potential telephone survey are as follows:

- 1) Caregiver does not have adequate knowledge of identified patient and/or does not participate in that member's healthcare decisions
- 2) Caregiver is not English or Spanish speaking

- 3) Caregiver does not have adequate hearing to participate in telephone survey and is therefore not eligible for randomization.
- 4) Caregiver is not able to speak on a telephone
- 5) Caregiver is less than 21 years old

*Recruitment:* Potential subjects will be identified from the ED on the basis of the cognitive state of the ED patient. Family caregivers will be identified and approached in the ED and if not present, will be contacted by phone and offered participation in the study. Potential subjects (caregivers) are identified by the treating team who have no direct involvement in the research. As is typical for these kind of clinical studies, the treating team, using clear inclusion and exclusion criteria will ask potential subjects whether or not a research assistant (RA) (from the POISED team) can speak with them to tell them about an opportunity to participate in a study. The treating team is never informed as to whether a potential subject agrees to participate or refuses after meeting with the RA. Caregivers and/or care recipients who are in the ED will be approached only after we (the POISED team) are given permission from the ED staff who will alert the research assistant of a potential caregiver-care recipient dyad. Caregivers and their care recipients will be informed that declining to participate will in no way impact their care in the emergency department or elsewhere and that the treating medical staff will not know about their decision as to their agreement or refusal of participation.

After ED staff have completed cognitive assessment using the Mini-Cog™ and given us permission for to speak to the dyad, we will approach and offer participation to CGs and ED patients > 75 years who have scored <=3/5 on the Mini-Cog™ and have plans to be discharged home. A score of >3.4 on the Short IQ-CODE (a proxy tool used by ED staff) will identify those few who cannot complete the Mini-Cog™. We will consent CGs and care-recipients at the time of ED visit. (See Recruitment, Consent, and Assent). If the care recipient lacks capacity, we will attempt to consent to identify and consent the Care Recipient via a proxy (See Recruitment, Consent and Assent) If there is no available or identified CG, we will attempt to identify and consent the CG at a later date either by phone (using an IRB approved verbal consent telephone script with waiver of written documentation of consent) or in person using an IRB approved consent form to obtain written consent. Please note that the study team will maintain a deidentified record (using a linking code) of who had been approached (in person or by phone), whether they had declined or accepted to participate in the research, and at what time and on what date this conversation took place.

*Phone Recruitment:* In the event that ED recruitment and assessment cannot be done in person, a Phone Recruitment Protocol will take effect. Potential subjects will be identified from the ED on the basis of a recent admission to a participating ED site location, using the EMR. Family caregivers will be identified by the patient, or via the EMR (i.e. Emergency Contact). In order to contact a family caregiver, the person who was the ED patient will need to be called by telephone first. If the patient gives any indication of not wanting research staff to call their family member or emergency contact, research staff will not attempt to call that person and the patient and care partner will no longer be eligible to participate. A recruiter will attempt to contact the patient within 48 hours of their discharge from the ED to assess willingness to participate and our interest in contacting the designated care partner. When a Mini-Cog cannot be administered in person, the study team member will contact a Care Partner (if no refusal by the patient to do this) and will conduct the IQCODE with that care partner. After assessment for eligibility, informed consent will be obtained over the phone.

*Randomization:* A web-based randomization scheme will be used to randomize participants to intervention or usual care groups in blocks of four or six stratified by: site (NYU or IU), English or Spanish speaking, whether the care partner lives with the CR, and Mini-Cog™ score less than or equal to 3 (or IQCODE of >3.4).

. We assume a positive IQ-CODE score (>3.4) with an inability to complete a Mini- Cog™ is equivalent to a Mini-Cog™ score of 0.

*Initial assessment phase:* The POISED care management team consisting of specially-trained nurses functioning as care managers (CMs) and para-professionals in the role of care manager assistants (CMAs) will conduct a biopsychosocial/environmental needs assessment by phone within 48 hours of emergency room discharge if not possible during the ED stay. These team members are clinical professionals delivering a clinical service. They are not research staff or delivering experimental procedures. This assessment includes a demographic and psychosocial interview focused on achieving problem identification. The program uses standardized assessment tools including "Managing Your Loved One's Health" (MYLOH™) for chronic disease management and BEHAVE 5+ to identify problem behaviors common in advancing dementia that have been associated with caregiver strain, challenges to caregiving at home and in long-term care. BEHAVE 5+ also identifies proven behaviors common in prescribing of psychotropic medications to people with dementia. (See Appendix 3) If the consented CG is not available, we will attempt to complete the CG questions at a later date either by phone or in person.

*Root Cause Analysis:* Starting with the ED visit and working backwards in time, the team will explore and identify problems or branch-point situations that progressed to the need for ED care. Using a logic tree as a cause and effect approach to create a timeline of events leading to ED visit and asking the question, "how could this occur?" or "why" based on the "Five-Whys" strategy, the CM team will ask "why" for each successive answer, starting with "why did you come to the ED." Answers will be applied to medical record review looking for other possible triggers and opportunities for intervention. This brainstorming/investigative process to improve quality is also deployed by patient safety teams investigating adverse events.

*Usual Care Group:* The comparison group, those randomized to usual care (UC), will receive referrals to services at the time of enrollment. The usual care group will not receive the POISED structured assessment, attention to chronic disease management, or RCA related to the ED visit. Similar to intervention group, we will provide UC patients with a laminated card showing the Stress Thermometer™ (Appendix 5) for use in follow-up interview assessments.

**Specific Aim 1 Measures – Emergency Department (ED) Use:** We will obtain consent from patients to enable review of their medical records. We will identify all ED visits for the year prior to the index ED visit/study enrollment and for one year after enrollment. We will also search all-payer databases (APD) New York and the Indiana State Network for Patient Care to identify any episode of ambulatory or acute care that occurred within the 6 months of enrollment (6-month intervention and 6-month follow-up) and the 12 months prior to enrollment. Using the Care Recipient medical records, we will determine any prior diagnoses of dementia. We will also use the Care Recipient's medical records to determine comorbidity and root cause for ED use.

A one-item survey question will identify any additional visits that might have occurred outside the indicated state regions. For descriptive purposes, ICD discharge diagnoses will be included for any ED use. We will structure continuous variables that describe the number of ambulatory and/or acute care episodes.

**Aim 2: Develop a collaborative care plan with the interventional group and schedule follow up testing to assess whether the 6-month POISED intervention will improve family caregiver “activation” in managing the health care of care recipients compared with post-ED care without POISED at 3 and 6 months.**

*Strategy:* The POISED care management team consisting of specially-trained nurses functioning as care managers (CMs) and para-professionals in the role of care manager assistants (CMAs) will work to create an individualized care plan through the lens of cognitive impairment with an emphasis on coordinating care with the patient's primary care provider (PCP) and achieving relevance with the goals and capacity of the family CG and CR.

*First Follow up Visit:* After review of all findings from prior data and the first encounter, the CM and CMA create an initial plan and identify areas needing further assessment at the first home visit (within 2 weeks after enrollment). That visit enables the CM team to conduct some additional cognitive and functional testing while the RN uses the time to address more sensitive issues that the CG may be uncomfortable discussing in the presence of the CR. The results of this initial assessment and home visit are forwarded to the CR's PCP with requested feedback and further direction as needed

*Collaborative Care Plan Development Phase:* After the initial assessment is completed by the POISED care management team, any urgent issues are addressed, and consulting with the program geriatrician ([name] at NYU and [name] at Indiana University) and the PCP as needed, the CM rules in or out the diagnosis of dementia and its subtypes. The CM team maps out a proposed care plan and schedules a second home visit.

During the second home visit, the CM team reviews the identified problem list and seeks input from the CR and CG on this list and prioritizing those problems, issues or topics felt most important to be addressed first. From this consensus, the CM discusses a proposed plan of care and tailors interventions to the patients, and then explains the diagnosis, natural history, and the prognosis of dementia; implements care protocols; reviews, explains, and distributes corresponding educational handouts for the dyad; and connects patients and family CGs to in-home services and community resources as needed.

**Specific Aim 2 Measures – CG Activation in Health Care Management of CR:** After consenting the CG, we will measure caregiver activation, a multi-dimensional construct developed by [name] and colleagues that includes CG knowledge, skills, and confidence to manage a range of tasks and tackle challenges common to dementia health care management. Domains include recognizing, anticipating, and managing day-to-day symptoms and challenges for CR health; managing CR medications; recognizing and managing sudden changes in CR health; accessing health services and advocating for the CR in the health care space; and managing CG self-care. Four-level item responses range from “agree completely” to “disagree completely” with an additional option, “not my job”. We will use the total score to measure activation.

**Aim 3: Test whether POISED will improve caregiver psychosocial outcomes compared to post-ED care without POISED at 3 and 6 months.**

*Strategy:* Follow-up regularly in a scheduled manner with resources and interventions to continue supporting CG and CR

*The follow-up phase:* During the follow-up phase, the POISED care management team (primarily the CMA) will continue to interact with the CG and CR either face-to face at their home, through video, telephone, email, fax, or mail. The minimum amount of CMA contact during this time will be by telephone and will be weekly for the first month, twice monthly calls during the second and third months, and monthly calls for the following 3 months.

Interaction intensity will be dictated by presenting needs and circumstances. During these interactions, the CM or CMA will answer any questions generated from previous visits; collect CR and family CG feedback; have the family CG complete a brief assessment to identify need for specific care protocols; and facilitate family CGs' participation in an array of community services that are already available in either the New York or Indianapolis areas. The CM (nurse) will reconcile medications and review medication adherence at the initial and second home visit. Medication questions will be referred to the study pharmacist.

Throughout the duration of the follow-up phase, the team will continue to work with the CG/CR and the patient's primary care provider to monitor, implement, and adjust the individualized care plan as needed. Both NYU and IU have significant caregiver support resources, such as CG support groups, respite care, and individual telephone counseling support. The programs benefit from already developed field-tested services from prior work by both [name] and [name] (and in clinical application by [name] and [name]). Specific POISED features are highlighted here and included in Appendix 4

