***Inclusion/Exclusion Criteria for Care Recipients:***

Inclusion criteria for participation in care management or usual care are as follows:

- 1) Must be 75 years and older
- 2) Must be in the emergency department for care at the point of recruitment
- 3) Must be English- or Spanish-speaking
- 4) Must have a family member or friend who provides caregiving assistance
- 5) Must have a plan to be discharged to home
- 6) Must have scored < 4 on the MiniCogTM15-19 or if using caregiver assessment by IQCODE, must be > 3.4
- 7) Must have capacity to consent or have a proxy.

Exclusion criteria for participation in care management or usual care are as follows:

- 1) Care recipient (CR) is a resident of a nursing home or other supportive facility
- 2) CR scores  $\geq 3$  on the MiniCogTM or the caregiver assessment by IQCODE was  $< 3.4$
- 3) Caregiver (CG) declines participation
- 4) CR is not being discharged to home

CR does not allow their family member or emergency contact to be contacted

Note: If the care recipient lacks capacity and we cannot obtain consent from their proxy, we will not access those data or include them in any analyses. Please note that a caregiver can still participate in the study with the assent of the care recipient, without the use of the health care data.

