### **Recruitment, Consent and Assent**

Cognitive assessment is a usual care procedure for these emergency departments as part of the evaluation of patients 75 years and older who present to their emergency department. Eligible caregivers provide care for patients to be discharged home who perform poorly on the screening assessment defined by specific cut-points as abnormal (MiniCog™ < 3). If the patient is unable to be assessed but identified by the caregiver as having impairment consistent with likely dementia (IQCODE > 3.4) the caregiver will be considered eligible (see inclusion/exclusion criteria above, see page 3).

*The first stage of recruitment and consent is to determine the eligibility of the caregiver.* The caregivers of the eligible patients are considered for study recruitment and the caregivers will be approached in the ED or by phone (if Phone Recruitment in effect) and offered research participation. Only caregivers of those patients scheduled to be discharged home will be considered eligible for participation. If a caregiver is not present in the ED and a patient provides permission to contact that person, we will conduct consent procedures by telephone.

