#### Statistical Plan

We will compare randomization results to the pre-planned schedule, to ensure randomization integrity. To verify the comparability of the randomized groups, we will compare dyads to identify differences between their baseline characteristics (age, gender, race, education), CR comorbid medical conditions, and the Charlson comorbidity index. We will also look for differences in the number of primary care visits and acute care use during the year prior to enrollment between POISED and the usual care group by using analysis of covariance (ANCOVA) models for continuous variables and the Cochran-Mantel-Hansel statistic for categorical variables. We will control for stratification variables: recruitment site (NYU or IU), English vs Spanish (at NYU site), living arrangement (CG lives with CR or not), and cognitive status (Mini-CogTM score of a 3 or less). A cutoff of 0 or 1 is more strongly associated with functional disability than a cutoff of 3. Subjects requiring the IQ-CODE with scores  $>3.4$  will be included with those with MiniCogTM scores =0 to reflect greater impairment for those who cannot complete the Mini-CogTM. We will examine the distributions of continuous variables and use transformation or nonparametric methods in cases of violation to the normal distribution assumption. We will also examine the frequency distribution of all categorical variables and use exact inference procedures in cases of zero or small cell size. We will use SAS 9.4 (SAS Institute, Carey, North Carolina) for all analyses.

Specific Aim 1: We will use logistic regression models to compare the rates of ED admissions during the 6-month intervention period following the index (recruitment) ED visit. ED readmission within 6 months will be used as a binary outcome in the logistic model and randomization group will be the independent variable while adjusting for all stratifying variables including site, language, living arrangement and CR cognitive status. Baseline characteristics that are shown to be unbalanced in univariate comparisons between the two groups will also be adjusted.

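### As worded, the cognitive stratification factor is true of every eligible care recipient, so it has one level, and the severity split it implies is never defined

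*Combined protocol and SAP*

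**What the plan says.** **Stratifier.** The Randomization paragraph (Methods) stratifies by site, language, and "whether the care partner lives with the CR, and Mini-Cog™ score less than or equal to 3 (or IQCODE of >3.4". The Statistical Plan lists the factors to control for and ends with "and cognitive status (Mini-CogTM score of a 3 or less".

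**Entry cuts.** Care-recipient inclusion criterion 6 reads "Must have scored < 4 on the MiniCog", with an IQCODE above 3.4 as the alternative route. Exclusion criterion 2 removes Mini-Cog scores of 3 or more. The Recruitment text approaches patients "who have scored <=3/5 on the Mini-Cog™ and have plans to be discharged home". The section Recruitment, Consent and Assent describes screening as "defined by specific cut-points as abnormal (MiniCog™ < 3".

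**Hints of a split.** The Statistical Plan remarks: "A cutoff of 0 or 1 is more strongly associated with functional disability than a cutoff of 3". Both it and the Randomization paragraph treat IQCODE cases as equivalent to a Mini-Cog score of 0, for patients who cannot complete the test.

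**Use.** The Aim 1 logistic model is fitted "while adjusting for all stratifying variables including site, language, living arrangement and CR cognitive status". The Aim 2 model names care-recipient cognitive status, and the Aim 3 model controls for the stratification variables. The Sample Size section says that stratification makes actual power higher than projected.

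**The concern.** Site, language and living arrangement are each written as a real division into two groups. The cognitive factor alone restates the condition for entering the trial. A factor that everyone satisfies cannot balance the arms, and its coefficient cannot be separated from the intercept.

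An analyst coding the Aims 1–3 models as written finds a constant column. The choices are then to drop it, to pick a cut after the fact, or to look up what the randomisation system used, and the plan does not say which. That is avoidable discretion in the primary model. The coding of IQCODE cases as score 0 serves a purpose only if severity levels exist inside the eligible range, yet none is defined.

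**Working it through.** **1. The plan's own power figure.** Inputs (Sample Size section): 320 per group, control rate 40%, odds ratio 0.62, significance level 0.05 (taken as two-sided). Intervention odds = 0.62 × 0.40/0.60 = 0.4133, so the rate is 0.4133/1.4133 = 29.25% and the difference is 10.75 points. Unpooled SE = √[(0.40×0.60 + 0.2925×0.7075)/320] = 3.74 points; power = Φ(10.75/3.74 − 1.96) = 82.1%. The pooled formula gives 81.7%. The stated 82% reproduces and does not use the cognitive factor.

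**2. Number of levels.**

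| Source | Eligible Mini-Cog scores | Is 3 or less true? |
|---|---|---|
| Inclusion criterion 6 (below 4) | 0, 1, 2, 3 | all |
| Recruitment (3 or less) | 0, 1, 2, 3 | all |
| Exclusion criterion 2 (3 or more excluded) | 0, 1, 2 | all |
| Recruitment, Consent and Assent (below 3) | 0, 1, 2 | all |

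These four wordings amount to two distinct cuts, 0–3 and 0–2. Patients entering by IQCODE above 3.4 satisfy the factor by its own parenthesis. It has one level in every case, and the design matrix of intercept, arm and this indicator has rank 2, not 3.

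**3. Strata.** As worded: 2×2×2×1 = 8, or 6 if Spanish applies only at NYU, as the Statistical Plan indicates. A real two-level split would give 16, or 12.

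**4. What the split might be.** With scores 0–3 eligible, a cutoff of 0 gives {0 and IQCODE} versus {1, 2, 3}; a cutoff of 1 gives {0, 1 and IQCODE} versus {2, 3}. With 0–2 eligible, these become {0 and IQCODE} versus {1, 2}, and {0, 1 and IQCODE} versus {2}. The documents do not choose.

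**5. Precision at stake (illustrative; assumptions not in the documents).** Assume a share q of 30–50% in the more impaired level and a 10–20 point gap in 6-month ED risk between levels. The SD of the between-arm difference in that share under unstratified allocation is √[2q(1−q)/320] = 3.62 to 3.95 points. Multiplying by the gap gives an SD of 0.36 to 0.79 points in the risk difference, which is 0.9% to 4.5% of its variance. Removing that variance moves Aim 1 power from 82.1% to between 82.4% and 83.8%. At 450 per arm (half of the 900 dyads named under Aim 1) it moves from 92.7% to between 92.9% and 93.7%. This is a risk-difference approximation. Simulating the logistic model at the two extreme assumption sets (320 per arm, 20,000 runs each) gave gains of 0.2 and 1.4 points.

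For Aims 2–3, 205/320 = 64%, so 205 is the number per group. A two-sample t-test with effect size 0.28 has 80.7% power, matching the stated 80%. If cognitive level explains an assumed 1–5% of the remaining variance, dividing 0.28 by √(1−R²) gives 81.1% to 82.7%.

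**The case against.** **Severity adjustment is already planned.** Specific Aim 3 Measures says the HABC-Monitor will be used to adjust for dementia symptom severity, and Appendix 1 schedules it at baseline. This stands and softens the consequence. But no model in the Statistical Plan names the HABC-Monitor, and it does not define the stratifier.

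**The analyst could enter the score.** The models refer to cognitive status, and the score-0 rule for IQCODE cases would make sense with a 0–3 covariate. That is a sensible repair, but the Statistical Plan defines the variable by the single category.

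**The system may already use a real split.** It may; the documents do not say. If so, only the text is deficient.

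**The levels could be Mini-Cog completed versus IQCODE used.** The text does not support this: IQCODE appears as a parenthetical equivalent, and such cases are merged with score 0.

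**The imbalance rule is a backstop.** "Baseline characteristics that are shown to be unbalanced in univariate comparisons between the two groups will also be adjusted". The listed comparisons cover demographics, comorbidity and prior health-care use, not the Mini-Cog, so it offers partial protection at most.

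A reader might also infer that the Randomization paragraph and the Statistical Plan conflict on coding IQCODE cases. The Statistical Plan's opening words reach everyone requiring the IQCODE, but it gives the same reason, inability to complete the test. What remains is a gap: phone recruits take the IQCODE because no Mini-Cog could be given in person, and neither section addresses their coding.

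**Conclusion.** The point holds as a defect of definition. Under both distinct entry cuts the stated factor has one level: it creates no strata, is constant in the Aims 1–3 models, and contributes nothing to the power benefit claimed for stratification. This rests on the documents alone.

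A reader might go further and conclude that randomisation is compromised, that the treatment estimate is biased, or that 82% power is not met. The documents support none of these. Allocation is still random within the other strata, and the power calculation does not involve the factor. Nor does the remark on a cutoff of 0 or 1 settle on 0–1 versus higher; it is equally compatible with 0 versus higher.

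The precision at stake is small, roughly 0 to 2 points of power, and that range depends on assumed shares, risk gaps and explained variance. The stronger reason to act is to remove an undefined choice from the primary model before unblinding.

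**What to change.** 1. State in the Randomization paragraph and the Statistical Plan the cognitive levels the web-based system actually uses, and use the same levels in the Aims 1–3 models.
2. If the system has only one level, replace the constant before unblinding with a pre-specified baseline severity covariate: the Mini-Cog score, or a stated split within the eligible range (0 versus higher, or 0–1 versus higher). Appendix 1 does not list the Mini-Cog among the variables. If the score was not stored, use the baseline HABC-Monitor, naming in advance which score or subscale. The baseline interview precedes randomisation, so this is a valid covariate. Leave randomisation already under way unchanged.
3. When defining the levels, say how phone recruits who were never given a Mini-Cog are coded, since the score-0 rule is justified only for those unable to complete it.
4. Separately, reconcile the Mini-Cog entry cuts in the care-recipient criteria, the Recruitment text, and Recruitment, Consent and Assent, which conflict at a score of 3.

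The cost is a few sentences and one or two model degrees of freedom. No new data are needed if the Mini-Cog score or the baseline HABC-Monitor is held.
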